#### **11.1.6 Visit 6: Week 12 (Day 84 -3/+5 Days) Visit – End of Treatment/Study Visit**

The following procedures will be conducted at this visit:

1. The Week 12 Acne-QoL will be completed by the subject and collected prior to any other study-related procedures.
2. Perform an abbreviated physical exam, including measurements of weight and vital signs (blood pressure, heart rate, respiration rate, and oral temperature). Any abnormal physical exam findings will be recorded.
3. The Evaluator will perform the efficacy evaluations including the Evaluator's Global Severity Score (EGSS), inflammatory lesion counts, and non-inflammatory lesion counts. The EGSS is performed prior to the lesion counting. Every effort should be made for the same qualified and validated Evaluator to perform the efficacy evaluations at all visits from Baseline to Week 12 for the same subject.
4. The Evaluator will perform Cutaneous Safety and Tolerability Evaluations.
5. Record changes in any concomitant medications / therapies since the previous visit under Prior and Concomitant Medications or Therapies. Check for prior and concomitant medications / therapies as per Section 9.4.
6. Record any new AEs reported spontaneously by the subject or changes in any ongoing AEs.

7. The study diary calendar will be collected and reviewed for compliance. Any missed doses or deviations should be reported.
8. The study drug technician will retrieve the study drug pump from the subject and weigh the pump (with the cap on) on a calibrated scale and record the weight to the nearest 0.1 gram.
9. Perform a Urine Pregnancy Test for all females who are pre-menses and females of childbearing potential.
10. Collect blood samples for routine laboratory analysis (CBC/Diff, serum chemistry, and serum pregnancy for pre-menses females and females of childbearing potential).
11. *Select Sites Only* – Obtain representative photographs of the face.
12. Exit the subject from the study and complete the end of study eCRFs.

## 11.2 Evaluation of Efficacy

The determination of efficacy will be based on evaluator-blinded assessments of the signs and symptoms of acne vulgaris. Evaluators must be a board-certified/board-eligible dermatologist or have appropriate documented experience and training, and be present for formal study training and validation at the Investigator Meeting (and/or Site Initiation Visit), or obtain a waiver from the Sponsor based on experience (or through additional training organized by the Sponsor).

The EGSS scores and lesion counts will be performed at each study visit. The EGSS scores will be collected *before* the Lesion Counts. All Subject assessments will be performed by a trained and validated Evaluator. Every effort should be made to have the same evaluator assess the same Subject at each visit. If this is not possible, every effort must be made for the same Evaluator to assess the Subject at both the Baseline and Week 12 visits.

### 11.2.1 Evaluator's Global Severity Score (EGSS)

The Evaluator's Global Severity Score (EGSS) will be a static assessment that is independent of the baseline score. The investigator will make the assessment without referring to the baseline value. Every effort should be made for the same evaluator to perform each study assessment for the same study subject, for consistency in evaluations.

Subjects are eligible if they have acne with a global severity of a 3 (moderate) or a 4 (severe) on the EGSS at the Baseline visit. The following scores will be used to describe the severity grade and subsequent score:

**Table 4. Evaluator's Global Severity Score**

Score	Grade	Description
0	Clear	Normal, clear skin with no evidence of acne vulgaris
1	Almost Clear	Rare non-inflammatory lesions present, with rare non-inflamed papules (papules must be resolving and may be hyperpigmented, though not pink-red)
2	Mild	Some non-inflammatory lesions are present, with few inflammatory lesions (papules/pustules only; no nodulocystic lesions)

3	Moderate	Non-inflammatory lesions predominate, with multiple inflammatory lesions evident: several to many comedones and papules/pustules, and there may or may not be one nodulocystic lesion
4	Severe	Inflammatory lesions are more apparent, many comedones and papules/pustules, there may or may not be up to 2 nodulocystic lesions

### 11.2.2 Lesion Counts

The facial area lesion counts will be taken from the subject's face (including the nose). The lesion count groups will be inflammatory and non-inflammatory. Facial inflammatory lesions (pustules, papules, and nodules) will be counted as follows: pustules and papules will be counted and recorded together, not separately; nodular lesions will be counted and recorded separately. Non-inflammatory lesions (open and closed comedones) will be counted and recorded together. The lesions counts will be collected at each visit and/or upon discontinuation. The following are definitions of each lesion type counted:

*Inflammatory lesions* are defined as follows:

Papule: An erythematous, raised, palpable lesion less than 5 mm in diameter  
 Pustule: An erythematous, raised, likely palpable lesion containing white exudate or pus less than 5 mm in diameter  
 Nodule: A deep-seated, erythematous, firm lesion greater than 5 mm in diameter

*Non-inflammatory lesions* are defined as follows:

Open comedone (blackhead): A widely dilated sebaceous follicle plugged with darkly pigmented sebum  
 Closed comedone (whitehead): A small, closed sebaceous follicle distended with sebum, with a white appearance

### 11.2.3 Other Assessments

#### *Photography*

At select sites, photographs of the face will be taken at Baseline and at Weeks 2, 4, 8 and 12. Only subjects who provide written photographic consent for facial photographs will be included in photography.

## 11.3 Evaluation of Safety

Safety assessments will be conducted at baseline and each subsequent visit.

### 11.3.1 Cutaneous Safety Evaluations

Cutaneous safety will be evaluated through assessment of scaling, erythema, hypo-pigmentation and hyper-pigmentation at the drug-application site at the time of the visit. Cutaneous tolerability will be evaluated through assessment of selected local signs and symptoms at the drug-application site: itching, burning and stinging, as an average since the last visit.

Cutaneous safety and tolerability signs and symptoms that result in the subject requiring a concomitant therapy, interruption of treatment, or discontinuation from the study, will be reported as an AE.

(Note: To be assessed by the evaluator at the time of the study visit.)

*Scaling:*

0 – None	No scaling
1 – Mild	Barely perceptible, fine scales present on limited areas of the face
2 – Moderate	Fine scale generalized to all areas of the face
3 – Severe	Scaling and peeling of skin over all areas of the face

*Erythema:*

0 – None	No evidence of erythema present
1 – Mild	Slight pink coloration
2 – Moderate	Definite redness
3 – Severe	Marked erythema, bright red to dusky dark red in color

*Hypo-pigmentation:*

0 – None	No evidence
1 – Mild	Slight, barely perceptible
2 – Moderate	Definite, evident
3 – Severe	Marked, prominent

*Hyper-pigmentation:*

0 – None	No evidence
1 – Mild	Slight, barely perceptible
2 – Moderate	Definite, evident
3 – Severe	Marked, prominent

### 11.3.2 Tolerability Evaluations

To be reviewed with the subject at the study visit as average over the period since the previous visit.

*Itching:*

0 – None	No itching
1 – Mild	Slight itching, not really bothersome
2 – Moderate	Definite itching that is somewhat bothersome
3 – Severe	Intense itching that may interrupt daily activities and/or sleep

*Burning:*

0 – None	No burning
1 – Mild	Slight burning sensation; not really bothersome
2 – Moderate	Definite warm, burning sensation that is somewhat bothersome

3 – Severe Hot burning sensation that causes definite discomfort and may interrupt daily activities and/or sleep

*Stinging:*

0 – None	No stinging
1 – Mild	Slight stinging sensation, not really bothersome
2 – Moderate	Definite stinging sensation that is somewhat bothersome
3 – Severe	Stinging sensation that causes definite discomfort and may interrupt daily activities and/or sleep

### **11.3.3 Medical History and Abbreviated Physical Examination**

A medical history will be taken at Screening, and confirmed and revised if needed, at Baseline. Medical histories having resolved two or more years before Baseline need not be collected unless considered relevant by the investigator.

An abbreviated physical examination including measurements of height and weight, and vital signs (blood pressure, heart rate, respiration rate, and oral temperature) will be performed at Baseline and Week 12 (end of treatment/study). Any abnormal physical exam findings will be recorded. Note: Height measurement will only be performed at Baseline.

### **11.3.4 Laboratory Tests**

Clinical laboratory analyses (CBC/Diff and serum chemistry) will be conducted on blood samples collected from subjects at Baseline and Week 12 visit. All results will be reported, including results that are abnormal. Clinically significant results, in the opinion of the investigator, should be reported as AEs. If an AE should require laboratory testing, the results of the test must be obtained by the investigative site and filed in the subject's documentation.

For pre-menses females and females of childbearing potential, a serum pregnancy test will be conducted at Baseline and Week 12.

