#### **11.1.2 Visit 2: Baseline Visit (Day 0)**

If a washout is not needed, this visit may occur on the same day as the Screening Visit (Visit 1). If a washout is needed, Baseline Visit (Visit 2) must occur after the appropriate washout period based on the criteria provided in Section 8.2.

The following procedures will be conducted at this visit:

1. The baseline Acne-Specific Quality of Life Questionnaire (Acne-QoL) will be completed by the subject and collected prior to any other study-related procedures.
2. Record any changes in medical history since screening.
3. Record changes in any concomitant medications or therapies since the previous visit under Prior and Concomitant Medications or Therapies. Check for prior and concomitant medications / therapies as per Section 9.4.
4. Perform a Urine Pregnancy Test for all females who are pre-menses and females of childbearing potential. The urine pregnancy tests will be supplied by the CRO or CRO vendor.
5. Perform an abbreviated physical examination, including height and weight, and vital signs (blood pressure, heart rate, respiration rate and oral temperature). Note: height will only be measured at baseline, and not subsequent visits. Any abnormal physical exam findings will be recorded.
6. Verify that the subject continues to meet the applicable inclusion/exclusion criteria as outlined in Sections 8.1 and 8.2.
7. The Evaluator will perform Baseline efficacy evaluations including the Evaluator's Global Severity Score (EGSS), inflammatory lesion counts, and non-inflammatory lesion counts. The EGSS is performed prior to the lesion counting. Every effort should be made for the same qualified, validated Evaluator to perform the efficacy evaluations at all visits from Baseline to Week 12 for the same subject.
8. The Evaluator will perform Cutaneous Safety and Tolerability Evaluations.

9. Collect blood samples for routine laboratory analysis (CBC/Diff, serum chemistry, and serum pregnancy for pre-menses females and females of childbearing potential).
10. *Select Sites Only* – Obtain representative photographs of the face.
11. Assign the subject the presented kit number (this number will be generated from the Interactive Web Response System, [IWRS]).

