12. The study coordinator or designee will weigh the pump (with the cap on) to the nearest 0.1 gram on a calibrated scale and dispense to the subject. A study diary calendar will also be dispensed and the subject will be instructed to bring it in for their subsequent visits.
13. The study coordinator or designee will instruct the subject on the proper application procedure for the study drug per Section 10.1.3, and will provide written subject use instructions to the subject (Appendix 17.1). For the first application, the subject will apply the study drug at the investigational center under the direction of the study coordinator or designee. The study drug should be applied after all clinical assessments. The study coordinator or designee will instruct the subjects to apply the study drug once daily at home in the evening up to evening prior to Week 12 visit (study drug will not be applied in the evening after this study visit).
14. The study coordinator will instruct the subject to use a Sponsor/Investigator-approved, non-medicated sunscreen of at least SPF 15, and to wear protective clothing during the day (e.g., hat). Remind subject not to use study treatment on skin that may become eczematous during the study.
15. Record any AEs or changes in AEs since the screening visit and/or reported spontaneously by the subject.
16. Schedule the next study visit at Week 2 (Day 14 ± 3 days). Remind the subject to not apply study drug on day of next study visit, prior to the clinic visit.

**NOTE:** At the Baseline and Week 12 visits, serum pregnancy testing is **mandatory** for all pre-menses females and females of childbearing potential.

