## **11.4 Adverse Events**

### **11.4.1 Definition of Adverse Event**

An AE is any untoward medical occurrence in a patient or clinical investigation subject administered a medicinal product and which does not necessarily have a causal relationship with the study drug. AEs include any unfavorable and unintended illness, sign, symptom, clinically significant laboratory test abnormality, or disease temporally associated with the use of a

medicinal product that has appeared or worsened during the course of the clinical trial, regardless of causal relationship to the study drug(s) under study. AEs include any illness, sign, symptom, or out-of-range and clinically significant laboratory finding that has appeared or worsened during the course of the clinical trial, regardless of causal relationship to the study. The collection of non-serious AEs and serious adverse events (SAEs) will begin following the subject's completion of the consent process to participate in the study.

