### **12.2.1 Adverse Events**

All AEs occurring during the study will be recorded and classified on the basis of MedDRA terminology. Descriptions of AEs will include the date of onset, the date the AE ended, the severity of the AE, the relationship to study drug, the action taken regarding study drug usage, the action taken to treat the AE, and the outcome. All reported treatment-emergent AEs (TEAEs) will be summarized by the number of Subjects reporting AEs, system organ class, preferred term, severity, seriousness, and relationship to study drug. TEAEs are those AEs with an onset on or after the date of the first study drug application.

Adverse events will be summarized by treatment group and severity. Each subject will be counted only once within a system organ class or a preferred term by using the adverse events with the highest severity within each category.

Adverse events will be summarized by treatment group and relationship to study drug. Each subject will be counted only once within a system organ class or a preferred term by using the adverse events with the greatest relationship within each category.

Comparisons among treatment groups will be made by tabulating the frequency of subjects with one or more AEs (classified into MedDRA terms) during the study. The Fisher's Exact test will be used to compare the percentage of subjects in each treatment group who report any adverse event at a significance level of 0.05. The specific system organ classes and preferred terms analyzed will be those that are reported by at least one percent of the subjects in any treatment group.

All information pertaining to AEs noted during the study will be listed by subject, detailing verbatim given by the investigator, preferred term, system organ class, start date, stop date, severity, actions taken, and drug relatedness. The AE onset will also be shown relative (in number of days) to the day of initial dose of the randomized study drug.

Serious adverse events (SAEs) will be tabulated by subject within treatment groups.

In addition, a list of subjects who discontinued from the study and a list of subjects who experienced SAEs will also be provided.

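### Baseline laboratory findings and other Day 0 events that precede the first application can be tabulated as treatment-emergent, because Section 11.3.4 has no Baseline exception and the TEAE rule works by date only

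*Combined protocol and SAP*

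**What the plan says.** **Laboratory rule.** Section 11.3.4 states: "Clinical laboratory analyses (CBC/Diff and serum chemistry) will be conducted on blood samples collected from subjects at Baseline and Week 12 visit". Later in the same paragraph it adds: "Clinically significant results, in the opinion of the investigator, should be reported as AEs". It does not separate the two visits.

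**AE definition.** Section 11.4.1 counts as an AE an "out-of-range and clinically significant laboratory finding that has appeared or worsened during the course of the clinical trial". It starts the AE period before dosing: "The collection of non-serious AEs and serious adverse events (SAEs) will begin following" the subject's consent. Section 11.4.2 lists what is recorded for each AE. The timing items are the onset date and the end date, with no clock time.

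**Visit order.** In Section 11.1.2 (Baseline, Day 0), medical history is updated at step 2. Step 9 reads "Collect blood samples for routine laboratory analysis (CBC/Diff, serum chemistry, and serum pregnancy for pre-menses females and females of childbearing potential". The kit is assigned at step 11. Step 13 says "For the first application, the subject will apply the study drug at the investigational center", once the clinical assessments are done. AEs since Screening are recorded at step 15.

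**TEAE rule.** Section 12.2.1 states: "TEAEs are those AEs with an onset on or after the date of the first study drug application".

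**Medical history.** Section 11.3.3 states: "A medical history will be taken at Screening, and confirmed and revised if needed, at Baseline". Table 1, footnote 2, places that update before randomization.

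**The concern.** A Baseline sample drawn before the first application describes the subject before treatment. Anything found on it cannot have been caused by study drug. The plan uses these values as the reference for change from Baseline and for shift tables, yet Section 11.3.4 also sends clinically significant ones to the AE form, and the TEAE definition has no means of holding them back if they are dated to the day of the draw or later.

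What is at stake is the meaning of the TEAE tables. Pre-dose events would raise the rate in both arms and pull the ratio between them towards one. Because Sections 11.3.4 and 11.4.1 give different instructions for a Baseline result, sites may also handle the same finding differently. The Day 0 problem is not confined to laboratory results: any AE that starts on the day of the first application, but before it, is caught by the same rule.

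**Working it through.** The plan gives no figure on this point, so there is nothing to reproduce. The check is first a reading of the sections together, then an illustration on assumed rates.

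**1. Is the Baseline sample pre-dose on the date of first dose?** Yes. The draw is step 9 and the application step 13 of the same Day 0 visit (11.1.2).

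**2. Does the TEAE rule catch a pre-dose event on that date?** Yes. It includes the day of first application (12.2.1), and the listed AE data hold dates only (11.4.2). Onset is also shown in days relative to first dose, which identifies a Day 0 event but does not place it before or after the application.

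**3. Is a clinically significant Baseline result an AE?** Under 11.3.4 alone, yes. Under 11.4.1, only if it appeared or worsened during the trial. No safety laboratory test is scheduled at Screening (Table 1), and Screening can be up to 35 days before Baseline. A site therefore has no scheduled earlier study value to show whether the finding arose before or after consent.

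**4. Is there another place to record it?** Medical history, but its update is step 2, before the draw at step 9. Section 12.2.2 refers to a central laboratory. Turnaround is not stated; results probably arrive after the visit. The only explicit instruction for a significant result is then the AE rule in 11.3.4.

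**5. What onset date would it carry?** The documents do not say. The date of the draw or of the result makes it a TEAE; a date before Day 0 does not.

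**6. Size.** The plan gives 300 subjects per arm. Assumed, not from the documents: true TEAE rates of 25% (active) and 15% (vehicle), and a share q of subjects in each arm with a pre-dose finding recorded as a Day 0 AE, independent of other AEs.

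- Subjects with such a finding per arm = 300 × q.
- Observed rate = 1 − (1 − true rate) × (1 − q).

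| q | Findings per arm | Active | Vehicle | Difference | Ratio |
|---|---|---|---|---|---|
| 0 | 0 | 25.00% | 15.00% | 10.0 points | 1.67 |
| 1% | 3 | 25.75% | 15.85% | 9.9 points | 1.62 |
| 3% | 9 | 27.25% | 17.55% | 9.7 points | 1.55 |
| 5% | 15 | 28.75% | 19.25% | 9.5 points | 1.49 |

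At q = 3%: 1 − 0.75 × 0.97 = 0.2725 and 1 − 0.85 × 0.97 = 0.1755. Not all 9 findings per arm add a subject to the count, because some of those subjects have another TEAE anyway. The additions are 9 × 0.75 = 6.75 (active) and 9 × 0.85 = 7.65 (vehicle).

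**7. Effect on the planned test.** In whole subjects, 75 v 45 of 300 gives a two-sided Fisher p of about 0.003. With the q = 3% additions, 82 v 53 of 300 gives about 0.006. The conclusion on these assumptions is unchanged. For single terms, the 1% entry threshold is 3 of 300, and even 3 v 0 gives p = 0.25.

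The Fisher paragraph in 12.2.1 speaks of AEs during the study and does not say TEAEs. Read literally, a pre-dose AE enters that comparison whatever its onset date.

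**The case against.** The strongest answer is that 11.4.1 is the governing definition. A pre-existing abnormality first seen at Baseline has not appeared or worsened during the trial, so it need not be an AE and can go to medical history. The onset date is not fixed either. A reader might infer from 11.3.4 that every clinically significant Baseline result becomes an AE and is counted as treatment-emergent; the documents do not support that. This part of the objection stands. It does not remove the conflict, because 11.3.4 gives an unqualified instruction, the history update comes before the draw, and no scheduled Screening value exists to settle whether the finding is old.

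A reader might also infer that a persisting abnormality would be reported again at Week 12 and counted twice. That fails: 11.4.1 requires a finding to have appeared or worsened, and the severity and relationship tables in 12.2.1 count each subject once within a system organ class or preferred term.

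There are partial safeguards. Causality is assessed for every AE, so a pre-dose finding should be judged not related and stay out of the drug-related counts. Shift tables handle Baseline laboratory status properly. These protect the related-AE and laboratory tables, not the overall TEAE counts.

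Finally, Section 12 refers to a separate SAP with fuller detail. The text available here does not contain it, so a Day 0 rule there cannot be ruled out.

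**Conclusion.** The point holds as a classification gap. Section 11.3.4 does not match 11.4.1 for Baseline results, and the TEAE rule cannot separate pre-dose from post-dose events on Day 0. A pre-dose finding recorded as an AE and dated Day 0 or later would be tabulated as treatment-emergent.

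The importance is minor. These events precede exposure in a randomized trial, so they should balance between arms on average: the expected effect is slightly higher TEAE rates in both arms and a slightly diluted ratio, not a bias towards one treatment. Over assumed shares of 1% to 5%, the difference falls from 10.0 to between 9.9 and 9.5 points, and the ratio from 1.67 to between 1.62 and 1.49. This rests on assumed TEAE rates, an assumed frequency of Baseline findings, independence from other AEs, and sites choosing to record the findings as Day 0 AEs. No efficacy result is affected.

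**What to change.** **Section 11.3.4, reconciled with 11.4.1.** State that:

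- a clinically significant Baseline result is recorded as medical history, which may be added after the visit when the result arrives;
- if there is evidence that it arose after consent, it is recorded as a pre-treatment AE and is not a TEAE;
- a Week 12 result is an AE if it is clinically significant and new or worse than Baseline.

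This keeps AE collection from consent.

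**eCRF.** Add one field for AEs with a Day 0 onset: before or after the first application. Complete it at the existing step 15 AE review. Do not move that review ahead of dosing, since it is the visit's only listed AE check after the first application.

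**Section 12.2.1.** Define TEAEs as AEs with onset after the first application, counting Day 0 events only when flagged as after. Say whether the Fisher comparison uses TEAEs; otherwise the new definition does not reach it. Carry the same wording into the SAP.

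**Cost.** A few sentences and one eCRF field. TEAE counts will be slightly lower in both arms.
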